#### 11.1.1 Response Criteria for AIHA

See [Appendix B: AIHA Response Criteria](#)for the definition of clinical response for AIHA.

### 11.2 Secondary Endpoint(s)

Objective	Endpoint	Start	End
Evaluate acalabrutinib's ability to induce short term and sustained hemoglobin response	AIHA ORR after 3 and 12 cycles	First dose of study drug [i.e., C1 Day 1]	After 12 cycles of treatment
	Frequency of PRBC transfusion while receiving acalabrutinib		Up to 30 days after last dose
	AIHA-specific Relapse-Free Survival (RFS)		Until time of AIHA relapse, death, or end of follow-up, whichever occurs first. [up to 12 months after the last dose of study drug]
	AIHA Sustained Response		
Assess the toxicity of acalabrutinib	Incidence and type of treatment-related toxicity [per CTCAE v5.0 and IWCLL 2018 criteria  ]		Up to 30 days after last dose of study drug
Evaluate efficacy of acalabrutinib in CLL	CLL ORR after 6, 12 cycles, per standard IWCLL criteria	First dose of study drug [i.e., C1 Day 1]	After 6 or 12 cycles from treatment start
	CLL-specific event-free survival (EFS)		Until time of progression, death, start of new therapy, or end of follow-up, whichever occurs first. [up to 12 months after the last dose of study drug]
	Duration of CLL response	When CR/PR is first documented	

AIHA ORR after 3 and 12 cycles: it will be defined as the proportion of patients achieving AIHA CR/PR after 3 or 12 cycles respectively. Patients evaluable for this endpoint include: 1) those who receive at least 3 or 12 cycles of acalabrutinib treatment and have AIHA response evaluation after 3 or 12 cycles; 2) patients

who terminate acalabrutinib prior to completing 3 or 12 cycles due to relapse of AIHA or CLL progressive disease (they will be counted as non-responders).

Frequency of PRBC transfusion: it will be defined as the number of PRBC transfusions from start of protocol treatment through EOT.

*AIHA-specific Relapse-Free Survival (RFS):* it will be defined as the time from start of acalabrutinib treatment until death, or relapse of AIHA. Patients without death, or AIHA relapse will be censored at the last follow-up or when they begin new therapy for CLL or AIHA. **Relapse of AIHA will be determined by the investigator. A minimal requirement is Hgb<10 g/dL and evidence of hemolysis per laboratory parameters.** Investigators will document the criteria by which relapse was assessed.

*Toxicity:* incidence, type, severity, and attribution of toxicities on the study will be assessed by CTCAE v5.0 (non-hematologic) and IWCLL 2018 (hematologic). All patients who receive at least 1 dose of acalabrutinib will be included in the toxicity analysis.

*CLL ORR after 6 or 12 cycles:* it will be defined as the proportion of patients achieving CLL CR /PR after 6 or 12 cycles respectively. Patients evaluable for this endpoint include: 1) those who receive at least 6 or 12 cycles of acalabrutinib and have a CLL response evaluation at those timepoints; 2) patients who terminate acalabrutinib treatment prior to completing 6 or 12 cycles due to CLL progressive disease (they will be counted as non-responders).

*CLL-specific Event-free Survival (EFS):* it will be defined as the time from start of acalabrutinib treatment until death, time of CLL progression, or start of new therapy for CLL, whichever earlier. Patients without death, CLL recurrence/progression, or start of new therapy for CLL will be censored at the last follow-up.

*Duration of CLL-response:* it will be estimated among patients who achieve CLL CR/PR on protocol treatment. It will be defined as the time from the first documented CLL CR/PR until death, time of CLL recurrence/progression, or start of new therapy for CLL, whichever earlier. Patients without death, CLL recurrence/progression, or start of new therapy for CLL will be censored at the last follow-up.

*AIHA sustained response:* it will be estimated among patients who achieve AIHA CR/PR on protocol treatment. It will be defined as the time from the first documented AIHA CR/PR until death or relapse of AIHA, whichever is earlier. Patients without death or AIHA relapse will be censored at the last follow-up or when they begin new therapy for AIHA or CLL.

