##### Nature of Illness and Illness Related Criteria

\_\_\_4. "Warm" or "cold" AIHA in patients with CLL, relapsed/refractory (RR) after first line treatment with oral prednisone (with or without rituximab), defined as:

- anemia ( $Hgb \leq 10$  g/dL; or  $Hgb > 10$  g/dL dependent on transfusions or maintenance therapy (rituximab, cyclosporin, etc) to maintain this level of hemoglobin, and
- laboratory evidence of hemolysis – presence of 3 of 4 markers (increased reticulocyte count, increased indirect bilirubin, increased lactate dehydrogenase, absent haptoglobin)

\_\_\_5. Positive DAT (score  $\geq 1+$ ) – either IgG DAT, C3 DAT, or both. Eligibility of patients with Coombs-negative AIHA should be confirmed by the trial investigator at each respective study site.

\_\_\_6. Histologically or flow cytometry confirmed diagnosis of CLL/SLL

\_\_\_7. Participant must be able to swallow tablets or capsules.

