#### 12.2.1 Analysis Populations

The evaluable patients for the clinical endpoints will be eligible participants who received at least 1 dose of protocol treatment, unless otherwise specified in Section 11.1 under the specific/particular endpoint.

The evaluable patients for the exploratory endpoints will be eligible participants who received at least 1 dose of protocol treatment and has at least 1 correlative blood specimen collected on the study.

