### 12.4.2 Analysis of the Secondary Endpoints

The probability of having AIHA-ORR at 3 or 12 cycles will be measured and reported with 95% exact confidence interval. AIHA-specific RFS will be estimated using Kaplan-Meier methods along with 95% confidence interval.

The CLL-ORR after 6 and 12 cycles will be assessed and reported with 95% CI. The Kaplan-Meier method will be used to estimate CLL-specific PFS and DOR, and the summary statistics (e.g., 12-month survival, median survival, 95% confidence intervals) will be provided. DOR will be estimated only among responders (i.e. participants achieving CLL CR/PR at least once).

The frequency of PRBC transfusion will be summarized by descriptive statistics. The difference between the average number of PRBC transfusion per month during protocol treatment vs. the average number of PRBC transfusion at baseline (in the past 6 months before protocol treatment, if available) will be assessed by paired t-test.

Toxicity events will be tabulated and summarized using descriptive statistics such as count and percentages, by severity, attribution, and system organ class according to the CTCAE v5.0 (non-hematologic) and by severity according to IWCLL 2018 (hematologic).

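### Both AIHA durability endpoints censor at new AIHA therapy, so a failing patient switched without a declared relapse is not counted and durability reads too high to that extent

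*Combined protocol and SAP*

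**What the plan says.** All four time-to-event definitions stand in section 11.2.

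- **AIHA-specific RFS** runs from the start of acalabrutinib to death or AIHA relapse. "Patients without death, or AIHA relapse will be censored at the last follow-up or when they begin new therapy for CLL or AIHA".
- **AIHA sustained response** runs from first documented AIHA response, among responders, to death or relapse. "Patients without death or AIHA relapse will be censored at the last follow-up or when they begin new therapy for AIHA or CLL".
- **CLL-specific EFS** runs "until death, time of CLL progression, or start of new therapy for CLL, whichever earlier".
- **Duration of CLL response** runs "until death, time of CLL recurrence/progression, or start of new therapy for CLL, whichever earlier".

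The investigator determines AIHA relapse, subject to a floor: "A minimal requirement is Hgb<10 g/dL and evidence of hemolysis per laboratory parameters". The criteria used must be documented.

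For the analysis, section 12.4.2 says "AIHA-specific RFS will be estimated using Kaplan-Meier methods along with 95% confidence interval". It does not name AIHA sustained response, which is covered only by the general Kaplan-Meier text in 12.4. No sensitivity analysis of the censoring rule is planned. Sections 5.1 and 5.8 allow follow-up and participation to end when a new AIHA or CLL treatment begins, and both name standard-of-care BTK inhibitors as such a treatment.

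**The concern.** Kaplan-Meier treats a censored patient as having the same outlook as those still under observation. A patient moved to another AIHA treatment because acalabrutinib is not controlling the hemolysis does not have that outlook. If relapse was not declared first, the failure leaves the analysis as a censored time. A later relapse may never be seen, because follow-up may stop at the switch.

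The documents leave at least two routes to an undeclared failure:

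- Section 12.3 foresees patients stopping in cycle 1 because the drug appears not to be working, and does not call this relapse. This route bears on RFS, since such patients are unlikely to have responded.
- A patient held at Hgb 10 g/dL or above by transfusion cannot meet the relapse floor at that value. Inclusion criterion 4 admits patients above 10 g/dL who are "dependent on transfusions or maintenance therapy (rituximab, cyclosporin, etc) to maintain this level of hemoglobin".

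These two endpoints carry the time-to-event evidence for the sustained part of the hemoglobin-response objective.

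**Working it through.** **Step 1. Text comparison.** Duration of CLL response is the direct counterpart of AIHA sustained response: both start at first documented response and both are restricted to responders. New therapy for the disease in question is an event in the first and a censoring time in the second. The End column of the 11.2 table shows the same split, listing new therapy for CLL EFS but not for AIHA RFS. No reason is given.

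**Step 2. The plan's own figures.** The documents give no expected value for either AIHA durability endpoint. The only design figure is for the primary test (10 or more responders of 20, null 0.30, alternative 0.60). An exact binomial calculation gives alpha 0.0480 and power 0.8725, matching the stated 0.048 and 87%. Nothing below depends on it.

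**Step 3. Formula.** With no other losses before month 12, S(12) is the product of (1 − 1/n) over the failures, where n is the number at risk at each. If one failure is censored instead, its factor (n − 1)/n drops out and later risk sets are unchanged. The estimate is therefore multiplied by n/(n − 1), so it can only rise.

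**Step 4. RFS, assumed data.** 22 treated (the planned enrollment), 13 responders, 9 non-responders who fail between months 1.5 and 5.5, and 3 declared relapses between months 7 and 11. Everyone else is followed past month 12.

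- All 12 failures counted: 10/22 = 45.5%.
- One non-responder failure censored: from 10/22 × 22/21 = 47.6% (earliest failure) to 10/22 × 14/13 = 49.0% (latest). The average over the nine positions is 48.2%, a rise of 2.7 points.
- Two censored: average 51.1% (50.0% to 52.4%).
- Four censored: average 57.4% (55.6% to 59.4%).

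With 7 responders and 2 relapses instead, the figures are 5/22 = 22.7% with none censored, 24.5% with one and 26.5% with two.

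**Step 5. Sustained response, assumed data.** 13 responders and 3 declared relapses.

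- No undeclared switch: 10/13 = 76.9% under either rule.
- One undeclared switch: 9/13 = 69.2% as an event. As censored, 9/13 × 13/12 = 75.0% to 9/13 × 10/9 = 76.9%, average 75.9%. The difference is 6.7 points (5.8 to 7.7).
- Two undeclared switches: 8/13 = 61.5% as events; as censored, average 74.7% (72.7% to 76.9%). The difference is 13.2 points.

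**Step 6. Can the opposite rule overshoot?** Suppose every new AIHA therapy were an event. Planned treatment lasts 12 × 28 = 336 days, about 11.0 months. If 3 of the 10 event-free patients in step 4 moved to a standard-of-care BTK inhibitor just after month 11 and were scored as failures, RFS would read 7/22 = 31.8%. The present rule gives 45.5%.

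**The case against.** The strongest objection concerns the remedy. A responder who completes planned therapy and continues BTK inhibition as standard care has not failed. In a patient with both diseases, that switch may not be for CLL alone. A reader might infer from the CLL definitions that all new AIHA therapy should be an event. Sections 5.1 and 5.8 do not support that, and step 6 shows the possible cost. Continuation on study to 36 cycles (5.3) may keep such switches few. This objection stands, and the event has to be tied to the reason for the switch.

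Other points, and what remains of them:

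- **Relapse may usually be declared.** Hemolysis parameters are scheduled at treatment visits and at end of treatment. Section 5.6 lists AIHA relapse as a removal reason and has no separate lack-of-efficacy item. The affected group may therefore be small or empty.
- **Hgb of 10 g/dL or above is not failure in itself.** Appendix B accepts untransfused Hgb at that level as partial response. A reader might infer that every switch at 10 or above is a hidden failure; the argument holds for patients kept there by transfusion.
- **Naming explains part of the contrast.** An event-free endpoint commonly counts new therapy and a relapse-free one need not. That can account for EFS against RFS, but not for the two duration-of-response endpoints.
- **The effect on RFS is small against its precision.** A shift of 2.7 points compares with a Greenwood standard error of √(0.455 × 0.545/22), about 10.6 points. That is fair, but imprecision does not justify a rule that can err only upward for these patients.

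**Conclusion.** The point holds conditionally. The censoring rule is as described, and any failing patient switched without a declared relapse raises the Kaplan-Meier durability estimate. On the assumed data, one such patient adds about 3 points to 12-month RFS and about 7 points to sustained response. The responder counts, relapse counts and timings are assumptions, and the documents give no basis for the number of undeclared switches. If there are none, the bias is zero.

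A reader might infer that every switched failure is lost. That is not so, because a relapse declared before the switch is an event. A reader might also infer a bias from never-responders, since RFS starts at first dose and section 12.2.1 says "The evaluable patients for the clinical endpoints will be eligible participants who received at least 1 dose of protocol treatment". The text does not say how such patients are scored, so that gap alone fixes no direction and forms no part of this conclusion.

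The primary response test and sample size are unaffected, and both endpoints are descriptive. The change is worth making because it costs little and makes the durability estimates less open to informative censoring.

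**What to change.** In sections 11.2 and 12.4.2:

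1. In both AIHA endpoints, count as an event any new AIHA-directed therapy started for loss or lack of AIHA control, in line with the rule for duration of CLL response.
2. Keep as censored any therapy started for CLL alone, and any move to a standard-of-care BTK inhibitor while the AIHA response is ongoing.
3. State, for endpoint purposes only, whether the rescue steroids allowed under exclusion criterion 10 count as new AIHA therapy.
4. Record the reason for the first new therapy. Section 5.9.1 already asks for the reason when concomitant therapy is added or changed; the same item is needed for the first therapy after acalabrutinib.
5. Report the present censoring rule alongside as a sensitivity analysis, with the number censored or counted by reason.

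The cost is one extra data item, some reliance on the recorded reason for the switch, and durability figures that may be slightly less favourable. Sample size and the primary analysis do not change.

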## 5.6 Duration of Therapy and Criteria for Removal from Protocol Therapy

Participants will receive protocol therapy until one of the below criteria are met:

- Completed protocol therapy (see [Section 5.3](#))
- AIHA relapse or progressive disease for CLL
- Participant is deemed intolerant to protocol therapy because of toxicity, despite dose modification/delay
- General or specific changes in the patient's condition which render the patient unacceptable for further treatment in the judgment of the investigator
- Withdrawal of consent for further protocol therapy (See [Section 17.5](#))

Once participants meet criteria for removal from protocol therapy, the participant should then proceed to End of Treatment assessments, and then to follow-up (Refer to the Follow-Up section below).

Documentation of the reason for discontinuing protocol therapy and the date effective should be made in the Electronic Health Record/medical record and appropriate eCRF.

The COH DCC and the Study PI should be promptly notified of the change in participant status.

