
- n. Adverse events will be assessed using the [CTCAE v5.0](#) (non-hematologic) and IWCLL 2018 (hematologic). SAEs related to study procedures will be recorded and reported from the time the participant signs the Consent Form. Please see Section 14 for routine AE assessing and reporting ([Section 14.6](#)) and SAE reporting ([Section 14.7](#)).
- o. Electrocardiogram (ECG): resting 12-lead ECGs will be recorded at screening, and as clinically indicated throughout the study.
- p. A serum or urine pregnancy test is required during screening for women of childbearing potential. If urine pregnancy results cannot be confirmed as negative, a serum pregnancy test is required. For Day 1 Cycle 1, a pregnancy test may be omitted if previously obtained within 72 hours prior to first dose of trial treatment. Pregnancy tests (serum and/or urine tests) should be repeated, if required, per institutional guidelines. A serum or urine pregnancy test will be done for women of childbearing potential any time for missed or late menses, and at the end of treatment. If the urine pregnancy test is positive, a serum pregnancy test must be performed per institutional standards.
- q. Hematology: Hemoglobin; hematocrit; mean corpuscular volume (MCV); reticulocyte count (absolute and relative); leukocyte count; differential count; platelets. Additional hematology may be performed thereafter as clinically indicated
- r. Biochemistry: Comprehensive metabolic panel (CMP), including: Na, K, Cl, CO2, BUN, Creatinine, Ca, glucose, Albumin, Alkaline Phosphatase, total bilirubin, AST, ALT, total protein.
- s. Serum immunoglobulins, IgG, IgM, and IgA are required at screening and on cycle 13 D1.
- t. Hemolysis parameters: Reticulocytes, lactate dehydrogenase (LDH), bilirubin (direct/indirect), haptoglobin and DAT.
- u. Computed tomography (CT) scan of neck, chest, abdomen and pelvis per institutional guidelines (with intravenous contrast, wherever possible) will be performed for response assessment at screening, C7D1, C13D1 and annually thereafter. CLL response will be evaluated every time imaging is performed. A bone marrow biopsy will be performed only if CR is suspected. Positron emission tomography with CT (PET-CT) and/or magnetic resonance imaging studies may be performed as clinically indicated, per institutional guidelines, and is acceptable in place of CT, if performed.

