## 11.0 ENDPOINT DEFINITIONS/MEASUREMENT OF EFFECT

### 11.1 Primary Endpoint(s)

Objective	Endpoint	Start	End
Assess the efficacy of acalabrutinib in CLL patients with relapsed or refractory AIHA	AIHA ORR after 6 cycles [ORR defined as proportion of patients who achieve complete and partial response; refer to Appendix B ]	First dose of study drug [i.e. C1 Day 1]	After 6 cycles of therapy

Primary endpoint of AIHA ORR after 6 cycles will be defined as the proportion of patients achieving AIHA complete or partial response after 6 cycles. Patients evaluable for this endpoint include: 1) those who receive at least 6 cycles of treatment and have AIHA response evaluation after 6 cycles (each cycle = 28 days); 2) patients who terminate acalabrutinib prior to completing 6 cycles due to AIHA or CLL progressive disease (they will be counted as non-responders).

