#### 11.2.1 Response Criteria for AIHA and for CLL

See [Appendix B: AIHA Response Criteria](#) for the definition of clinical response for AIHA.

CLL response will be determined per the investigators' assessment, according to Hallek et al (see [Appendix C: CLL/SLL Response Criteria](#)). Response assessments are to coincide with CT measurements.

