## 12.5 Handling of Missing Data

Every attempt will be made to obtain data at the defined time points as described in the primary and secondary endpoints. If the data are not sufficient to analyze specific endpoints, the participant's data may be excluded entirely or partially, depending on the specific endpoints in question. No missing data will be imputed. Whenever possible, all available data will be included in the analysis. A sample size for each analysis will be clearly stated along with the reason for exclusion, if any participant is excluded from the analysis due to missing data.

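### CLL ORR at 6 and 12 cycles leaves out treated patients who stop early for any reason other than CLL progression, including those removed for AIHA relapse; an all-treated rate should stand beside it

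*Combined protocol and SAP*

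**What the plan says.** Section 11.2 defines two evaluable groups for CLL ORR after 6 or 12 cycles. The first is "those who receive at least 6 or 12 cycles of acalabrutinib and have a CLL response evaluation at those timepoints". The second is "patients who terminate acalabrutinib treatment prior to completing 6 or 12 cycles due to CLL progressive disease (they will be counted as non-responders". No other early stop is mentioned.

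Section 5.6 lists "AIHA relapse or progressive disease for CLL" among the criteria for ending protocol therapy, so either disease can take a patient off acalabrutinib.

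The AIHA response rates are scored differently. At 6 cycles (Section 11.1) the non-responders include "patients who terminate acalabrutinib prior to completing 6 cycles due to AIHA or CLL progressive disease (they will be counted as non-responders". At 3 and 12 cycles (Section 11.2) they include patients who stop early "due to relapse of AIHA or CLL progressive disease (they will be counted as non-responders".

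The footnote to the Section 10.0 calendar says that CT "will be performed for response assessment at screening, C7D1, C13D1 and annually thereafter", and the calendar row shows no CLL assessment at end of treatment. Section 11.2.1 adds: "Response assessments are to coincide with CT measurements". Section 12.5 states: "No missing data will be imputed". Section 12.4.2 reports CLL ORR with a 95% CI and no hypothesis test.

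**The concern.** A patient who relapses with AIHA before a CLL time point and is taken off drug has neither the required cycles nor CLL progression. That patient is neither a CLL responder nor a CLL non-responder at that time point; the patient is simply not counted. The same holds for stops due to toxicity, withdrawal, or death without CLL progression.

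CLL efficacy is a stated secondary objective in a trial whose patients are enrolled for AIHA. If AIHA failures drop out of the CLL denominator, the 12-cycle CLL ORR describes patients who stayed on drug for a year (plus CLL progressors), not the CLL patients who were treated. A reader of the result would probably assume the latter.

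The exclusion is also not neutral. Section 11.2 sets a minimum for AIHA relapse of hemoglobin below 10 g/dL with evidence of hemolysis. Appendix C requires untransfused hemoglobin of at least 11.0 g/dL for CLL CR, and all CR criteria must be met. Whether a patient is left out is thus tied to a component of the response being measured.

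**Working it through.** **The plan's own figure.** The only design calculation is for the primary endpoint: 10 or more responders of 20, null 0.3, alternative 0.6. The exact binomial gives a type I error of 0.04796 (stated 0.048) and power of 0.8725 (stated about 87%). It reproduces, and nothing below affects it. The documents give no expected rate or precision for CLL ORR.

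**Where an early stop goes, by reason and time.**

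| Reason for stopping before the time point | AIHA ORR | CLL ORR |
|---|---|---|
| CLL progression | non-responder | non-responder |
| AIHA relapse or progression | non-responder | not in denominator |
| Toxicity, withdrawal, death without progression | not in denominator | not in denominator |

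An exit before C7D1 is lost from both CLL rates. An exit between C7D1 and C13D1 has the C7D1 assessment, counts at 6 cycles, and is lost only at 12.

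**Can another section restore the patient?** No CLL assessment is scheduled at end of treatment, CLL response is tied to CT, and there is no imputation. Section 5.8 lets participation end when new AIHA therapy starts, so a later CT may not happen. Section 12.2.1 sets a default population of eligible patients with at least one dose, but yields to populations specified in Section 11.1. CLL ORR is in Section 11.2, so a literal reading keeps everyone in. Section 11.2 nevertheless states its own evaluable set for this endpoint, and the two conflict.

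**Size.** Inputs: N = 22 (Section 12.2, taking all 22 as eligible and treated). Assumed, because the documents do not give them: k, the exits outside the CLL rule before the time point; x, the CLL responders among the other 22 - k; and m, the CLL responders among the k exits.

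- Evaluable-only rate: x/(22 - k)
- All-treated rate: (x + m)/22
- Ratio: [x/(x + m)] × 22/(22 - k), which is largest at m = 0

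Maximum ratio: 22/20 = 1.10 for k = 2; 22/18 = 1.22 for k = 4; 22/16 = 1.38 for k = 6; 1 for k = 0.

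In percentage points, at the bound m = 0, with assumed response of about 60% or 80% among the remaining patients (Clopper-Pearson 95% intervals):

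| k | Evaluable only | All treated, m = 0 | Gap (points) |
|---|---|---|---|
| 2 | 12/20 = 60.0% (36.1-80.9) | 12/22 = 54.5% (32.2-75.6) | 5.5 |
| 4 | 11/18 = 61.1% (35.7-82.7) | 11/22 = 50.0% (28.2-71.8) | 11.1 |
| 6 | 10/16 = 62.5% (35.4-84.8) | 10/22 = 45.5% (24.4-67.8) | 17.0 |
| 2 | 16/20 = 80.0% (56.3-94.3) | 16/22 = 72.7% (49.8-89.3) | 7.3 |
| 4 | 14/18 = 77.8% (52.4-93.6) | 14/22 = 63.6% (40.7-82.8) | 14.1 |
| 6 | 13/16 = 81.3% (54.4-96.0) | 13/22 = 59.1% (36.4-79.3) | 22.2 |

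**Away from the bound.** Take k = 4 and x = 14, so the evaluable-only rate is 77.8%. If m = 0, 1, 2, 3 or 4 of the exits had a CLL response, the all-treated rate is 63.6%, 68.2%, 72.7%, 77.3% or 81.8%, and the gap is 14.1, 9.6, 5.1, 0.5 or -4.0 points. The gap closes when the exits respond about as often as the others.

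**The case against.** The strongest defence is that the rule is disease-specific on purpose. CLL-specific EFS and duration of CLL response in Section 11.2 likewise count only CLL events and death. AIHA relapse is not CLL progression, and Appendix C judges CLL response largely on nodes, liver and spleen, and lymphocytes. A patient in AIHA relapse cannot meet CLL CR at that moment but could still meet PR. CLL-specific EFS runs from first dose and keeps these patients, and Section 12.5 asks for the n of each analysis and the reason for any exclusion due to missing data. All of this stands. Asymmetry with the AIHA rule is not by itself an error, and AIHA relapse need not be labelled a CLL failure.

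A reader might also infer more than the documents support:

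- *That the CLL ORR is biased upward by some 15 points.* This comes from applying the 81% ORR of the randomized relapsed/refractory CLL trial in Section 2.2.1 to 18 of 22 patients: 0.81 × 18/22 = 66%. It assumes four exits and no CLL response in any of them, and borrows a rate from another population. It is a worst case, not an estimate.
- *That about 9 of 22 patients would leave this way.* The 60% design alternative implies 40% AIHA non-response, but Section 5.6 names relapse, not non-response. Sections 3.2 and 5.10.1 allow steroids on study, so a non-responder may stay on drug and remain evaluable for CLL.
- *That these patients have no CLL score at all.* Those who leave after C7D1 have one for the 6-cycle rate.
- *That an exact interval is distorted.* Section 12.4.2 names an exact interval for the AIHA rates; for CLL ORR it gives only a 95% CI.

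What the defence does not remove is the selected denominator. The plan gives no reason for it and no all-treated rate.

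**Conclusion.** The point holds as a gap in a stated rule. Patients removed for AIHA relapse before 6 or 12 cycles, and those who stop for toxicity, withdrawal or non-progression death, drop out of the CLL ORR at the time points they miss. Upward is the likely direction, resting on the hemoglobin conflict between AIHA relapse and CLL CR; it is not proven, since CLL PR remains possible. The number of exits and their CLL response are unknown, so only the bound 22/(22-k) can be given, and it vanishes at k = 0. In the worked cases (k = 2 to 6, no CLL response among exits) it amounts to about 5 to 22 points. The endpoint is secondary, descriptive and untested; the primary test and sample size do not change. This is a cheap improvement.

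**What to change.** In Section 11.2, define CLL ORR at 6 and at 12 cycles over all eligible patients who received at least one dose. Count anyone without a documented CLL CR or PR at that time point as not having achieved response, whatever the reason for stopping. Report the evaluable-only rate beside it, with its n and the reasons for each exclusion. This covers every type of exit without classing AIHA relapse as CLL progression. The same edit can bring the cross-reference in Section 12.2.1 into line with Section 11.2.

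The cost is a sentence or two of text, with no new visits or data. The headline CLL ORR will be somewhat lower. Some patients with an earlier CLL response who left for AIHA relapse will count as non-responders at the later time point. With no CLL assessment at end of treatment, the all-treated rate is a conservative figure, which is why both rates should be shown.
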